Changes in tumour biomarkers will be correlated with change in tumour size and other efficacy parameters.

Safety Analysis:

The Safety Analysis Set will be used for the analysis of safety data (AEs, including AESIs, clinical laboratory tests, vital signs, 12-lead ECGs, and physical examination). The safety data will be presented descriptively and not formally analysed.

Protocol version and date: Version 4.0 (25 April 2023)

STUDY SCHEMATIC

Figure 1 Study Schematic

AE=adverse event; CAFs=cancer-associated fibroblasts; IV=intravenously; PFS=progression-free survival; PO=per os (orally, or via either a feeding tube or a percutaneous endoscopic gastrostomy device in case patients are unable to swallow tablets); q3w=every 3 weeks; R=randomisation; RECIST v1.1=response evaluation criteria in solid tumours version 1.1

* For patients with a suitable archival tumour biopsy sample available, the archival sample may be used to assess CAFs level and determine eligibility (Note: this can only be performed after the patient has provided signed informed consent). This will not dispense from the need for a recent pre-study tumour biopsy. ** Or earlier if progression occurs before 9 weeks.

SCHEDULE OF ASSESSMENTS

Table 1Schedule of Assessments

Study Period	Screening		Double-blind Treatment Period			Follo	w-up ^a
Study Weeks:	-5 to -1	BL	3, 6, 9, 12, 15, 18, 21, 24, 27, 30, 33, 36, 39, 42, 45, 48, 51, 54, 57, 60, 63, 66, 69, 72, 75, 78, 81, 84, 87, 90, 93, 96, 99, 102	105	ЕоТ	Last IMP	Refer to
Study Days (Visit Window):	-35 to -1	1	Every 21 days (±5)	735 (±3)	Visit	(±7 days)	'L'
Visit:	1	2	3 to 36	37	ЕоТ	Safety Follow-up	Efficacy Follow-up
Informed consent	Х						
Determination of eligibility ^b	Х	\mathbf{X}^{b}					
Randomisation		Х					
Demographics, ECOG performance status, and relevant medical history	Х	Х					
Height	Х						
Body weight	Х		Х	Х	Х	Х	
Body temperature	Х	Х	Х	Х	Х	Х	
Physical examination / symptoms- directed physical examination ^c	Х	Х	Х	х	Х	Х	
Pulse rate, SBP, and DBP	Х	Х	Х	Х	Х	Х	
12-lead ECG ^d	Х	Х	Х	Х	Х	Х	
Blood sampling:							
Pregnancy test (serum) ^e	Xe						
Haematology and biochemistry ^f	Х	Х	Х	Х	Х	Х	
Thyroid function test ^f		Х	Х	Х	Х	Х	

Study Period	Screening		Double-blind Treatment Period			Follow-up ^a	
Study Weeks:	-5 to -1	BL	3, 6, 9, 12, 15, 18, 21, 24, 27, 30, 33, 36, 39, 42, 45, 48, 51, 54, 57, 60, 63, 66, 69, 72, 75, 78, 81, 84, 87, 90, 93, 96, 99, 102	105	ЕоТ	Last IMP	Refer to

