Treatment with pembrolizumab will continue until: RECIST v1.1-defined disease progression is determined by the investigator (Eisenhauer et al 2009), unacceptable toxicity, or a maximum of 24 months. If progression is suspected, but not confirmed, study treatment may continue until confirmation of radiological progression. Treatment with setanaxib or placebo will continue throughout the period of pembrolizumab therapy. When pembrolizumab is discontinued, blinded study treatment will also be discontinued.

Baseline assessments will be performed on Day 1 (Visit 2). Post-Baseline assessments will be performed every 3 weeks up to pembrolizumab discontinuation. Following permanent IMP discontinuation at any time during the study, patients will undergo an End-of-Treatment (EoT) Visit as soon as possible and a Safety Follow-up Visit at 28 days after the last dose.

Initial tumour imaging is performed within 35 days prior to the date of treatment and will be used as the Baseline scan for the tumour assessments. Tumour assessments will then be conducted from the date of randomisation and continue until RECIST v1.1-defined disease progression, irrespective of treatment discontinuation. Efficacy Follow-up for PFS and survival will continue until approximately 38 progression events have occurred. AEs will be recorded up to 28 days after study treatment discontinuation, while any further anti-cancer medication will be recorded until disease progression.

The primary endpoint is best percentage change in tumour size. A population with measurable disease will be selected to generate the maximum tumour response data. The secondary endpoints related to numbers of CAFs, CD8⁺ TILs, and regulatory T-cells in tumour tissue, and gene expression analysis in tumour tissue will be used to demonstrate the underlying mechanisms of action of setanaxib and support the primary objective.

Safety and tolerability data will be regularly reviewed by an unblinded IDMC, with the first assessment after approximately 12 patients (6 per treatment group) have had the opportunity to complete at least one cycle of pembrolizumab +/- setanaxib, followed by periodic assessments at a frequency defined in the IDMC Charter. The IDMC may recommend changes to the setanaxib dose regimen or study conduct based on the safety data reviews.

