10.4 Visit Windowing

For the purposes of the analysis, observations will be assigned to analysis visits using the windows detailed in Table 1. All visits (including unscheduled, EoT and safety follow-up visits) will be windowed to the appropriate analysis visit regardless of the visit label entered in the eCRF. Safety follow-up visits will only contribute to the Safety follow-up analysis visit. Tabulations will only summarise scheduled time points for the assessments.

If more than one quantitative measurement falls within a post baseline visit window, then the following rules will apply;

- For PK assessments, the latest value on or prior to the day of IMP administration within a given window will be selected. If there is more than one record on the selected day, then;
 - For Analysis Visit Week 9, the arithmetic mean of the assessments will be calculated.
 - For all other Analysis Visits, the latest pre-dose assessment will be used.
- For all other assessments, the value closest to the target day will be selected. If more than one assessment is equidistant from the target day, the assessment later in time will be selected. If more than one record remains, then the arithmetic mean of the assessments will be calculated.
 - ECG assessments are scheduled to be collected at pre-dose and post-dose timepoints on Study Day 1 and 22. Where multiple assessments occur on the same day in these instances, the timepoint will be preserved.
- If the EoT assessment and a scheduled assessment reside within the same visit window, the scheduled assessment will be selected.

If more than one quantitative measurement meets the Baseline definition (Section 10.1), then then the arithmetic mean of the assessments will be calculated.

If more than one qualitative measurement falls within a baseline or post-baseline visit window, then a conservative approach will be taken by selecting the worst result.

Analysis Visit	Target	Window for Safety	Window for Efficacy
Analysis Visit	Study Day		(Tumour Biopsies / Assessments)
Baseline	1		
Day 1	1		
Week 3	22	(±5)	
Week 6	43	(±5)	
Week 9	64	(±5)	(±7)
Week 12	85	(±5)	
Week 15	106	(±5)	(±7)
Week 18	127	(±5)	
Week 21	148	(±5)	(±7)
Week 24	169	(±5)	
Week 27	190	(±5)	(±7)
Week 30	211	(±5)	
Week 33	232	(±5)	(±7)
Week 36	253	(±5)	
Week 39	272	(±5)	(±7)
Week 42	295	(±5)	
Week 45	316	(±5)	(±7)
Week 48	337	(±5)	
Week 51	358	(±5)	(±7)
Week 54	379	(±5)	
Week 57	400	(±5)	(±7)
Week 60	421	(±5)	
Week 63	442	(±5)	(±7)
Week 66	463	(±5)	

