12.0 Statistical Methods

With the exception of the unblinded statistician and programmers supporting the IDMC, all personnel involved with the analysis of the study will remain blinded until the initial database soft lock at the time of the primary analysis. Further details on the blinding and unblinding are given in the study Blinding Plan.

In this study, it is planned to recruit approximately 35 investigational centres in USA and Europe. Unless specified otherwise, data from all participating sites will be combined for the analysis, so that an adequate number of patients will be available for analysis. In the event that a single site enrols a large proportion of patients, a site effect may be explored as described in Section 12.5.5, otherwise no site effect will be assessed.

All table summaries will be presented by treatment group (including an overall group for safety tables) and by analysis visit where appropriate. Unscheduled visits will be windowed as described in Section 10.4. Unscheduled visit values will contribute to any assessment of worst/most severe results, but otherwise will only be displayed in listings. Additional details related to specific presentations are given in programming notes of the supporting TFL shells.

Categorical variables will be summarised descriptively using counts and percentages. Percentages will be rounded to one decimal place, except 100%, which will be displayed without any decimal places and percentages will not be displayed for zero counts.

Continuous variables will be summarised using univariate statistics, including the number of observations (n), mean, standard deviation, median, minimum and maximum. The minimum and maximum values will be displayed to the same level of precision as the raw data, the mean and median to a further decimal place and the standard deviation to two additional decimal places. In addition, for tumour and biomarker summaries, the geometric mean and the interval of (geometric mean +/- geometric standard deviation) may also be presented.

Analyses will be performed using SAS® (SAS Institute, Cary, NC, US) version 9.4 or higher.

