12.6.3 Laboratory Data

Central laboratory data (haematology, serum chemistry, thyroid function) and local laboratory data (urinalysis) will be converted to Système International (SI) units. Any results containing the character values of "<" or ">" will be converted to the equivalent lower/upper limit of quantification (LLQ/ULQ). For each laboratory category and parameter noted in Table 4, absolute and change from baseline values will be summarised by analysis visit and treatment group using univariate statistics.

Shift tables of CTCAE grades from baseline to worst post-baseline will also be presented for the central laboratory data.

The change from baseline values for haematology, serum chemistry and thyroid function will be further summarised using box and whisker plots.

Standard reference ranges from the central laboratory will be used for the assessment of results being low, normal or high. Parameter results outside of the standard reference ranges will be flagged in the data listings.

Local laboratory urinalysis data will be listed only.

Table 4.	Laboratory	Parameters
----------	------------	------------

Category	Parameters			
Haematology	 Haematocrit Haemoglobin Absolute and Relative Reticulocyte Counts Red Blood Cell (RBC) Count White Blood Cell (WBC) Count Differential WBC Count 	 Platelet Count Absolute Neutrophil Count Mean Cell Volume International Normalised Ratio (INR) (Screening only). 		
Serum Chemistry	 Alkaline Phosphatase (ALP) Alanine Aminotransferase (ALT) Aspartate Aminotransferase (AST) Amylase Total and Conjugated Bilirubin Gamma-Glutamyltransferase (GGT) Glucose Total Protein 	 Albumin Creatinine Urea Total Cholesterol Triglycerides Sodium Potassium Chloride 		

Category	Parameters		
Thyroid Function	TSH and Free T4		
Urinalysis	pHProteinGlucoseKetones	 Bilirubin Blood Microscopic Examination of the Sediment 	
Pregnancy Test [†]	Serum Pregnancy TestUrine Pregnancy Test		

Note: Categories denoted with [†] will be listed only.

Note: WBC and Reticulocyte Counts will be expressed as absolute values. Differential counts will be expressed as both absolute counts and percentages of WBCs.

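### SAP 10.4 assigns every visit to an analysis visit, but the Table 1 safety windows leave gaps, so end-of-treatment and late-visit values that fall there have no row in the by-visit safety tables

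*SAP*

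**What the plan says.** SAP 10.4 (Visit Windowing) states that "observations will be assigned to analysis visits using the windows detailed in Table 1". It applies this to every visit type, naming unscheduled, EoT and safety follow-up visits, which "will be windowed to the appropriate analysis visit regardless of the visit label entered in the eCRF". It adds: "Tabulations will only summarise scheduled time points for the assessments". Its selection rules deal with several values inside one window. For most assessments the value closest to the target day is taken, and a scheduled value is preferred to an EoT value in the same window.

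SAP Table 1 gives safety windows of ±5 days for Weeks 3 to 102 and ±3 days for Week 105. Safety follow-up has its own row; EoT has none. Under SAP 10.2, study day for safety counts from the first dose of IMP.

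The by-visit outputs follow these windows. For laboratory data (SAP 12.6.3), "absolute and change from baseline values will be summarised by analysis visit and treatment group using univariate statistics". SAP 12.6.4 and 12.6.5 set out vital signs and ECGs in the same way.

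SAP 12.0 says "Unscheduled visits will be windowed as described in Section 10.4", and then "Unscheduled visit values will contribute to any assessment of worst/most severe results, but otherwise will only be displayed in listings".

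On timing, the protocol's schedule of assessments puts visits every 21 days with a 5-day allowance either way. After permanent IMP discontinuation, "patients will undergo an End-of-Treatment (EoT) Visit as soon as possible" (SAP 8.0). The EoT column of that schedule includes haematology, biochemistry, thyroid tests, vital signs and ECG.

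**The concern.** The ±5 days is the protocol's allowance for when a visit should take place. The SAP reuses it as the rule for where data go in the analysis, which is a different job. An analysis window has to accept whatever was actually collected; otherwise the statement that all visits are windowed cannot be carried out.

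EoT values are the clearest case. SAP 10.4 plainly means to use them, because it says what to do when an EoT and a scheduled assessment share a window. But an EoT visit happens when treatment stops, not on a grid day. Anaemia and hypothyroidism, the two events of special interest, can lead to permanent discontinuation (Protocol 5.3.2.1 and 5.3.2.2), so haemoglobin and TSH at EoT are results a reader would want in the tables. With about 25 patients per group, a few missing values can matter at later visits.

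The rule is also ambiguous to program. One programmer could leave gap values unassigned and another could move them to the nearest visit, and both could claim to follow the text.

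**Working it through.** **Inputs.** Target days and widths come from SAP Table 1, the day-count convention from SAP 10.2, and the visit allowance from the protocol's schedule of assessments. The SAP states no coverage figure, so there is none to reproduce.

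**One interval.** Week 3 is Day 22 ± 5, that is Days 17–27. Week 6 is Day 43 ± 5, that is Days 38–48. Days 28–37 belong to neither. In general a ±5 window covers 2 × 5 + 1 = 11 days, and a 21-day interval leaves 21 − 11 = 10 days.

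**All intervals.** Weeks 3 to 105 give 35 windows and 34 gaps between them:

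| Gap | Length (days) | Number |
|---|---|---|
| Regular | 10 | 31 |
| Days 259–266 (Week 36 to 39) | 8 | 1 |
| Days 278–289 (Week 39 to 42) | 12 | 1 |
| Days 721–732 (Week 102 to 105) | 12 | 1 |

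Unassigned days = 31 × 10 + 8 + 12 + 12 = 342. Days 17–739 contain 739 − 17 + 1 = 723 days, and 342 / 723 = 47.3%. Covered days check: 34 × 11 + 7 = 381, and 723 − 381 = 342. Days 2–16 (15 days) also have no window.

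**Which scheduled visits fall in a gap.** On the regular grid, a visit 6 to 15 days late does (for Week 3, 22 + 6 = 28 to 22 + 15 = 37). A visit 1 to 5 days late is still assigned. A visit 16 or more days late enters the next visit's window.

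**Week 39.** The other targets follow day = 1 + 7 × week. For Week 39 this gives 1 + 7 × 39 = 274, but Table 1 has 272. The SAP window is Days 267–277; five days either side of Day 274 is Days 269–279. Days 278 and 279 are therefore within the allowance but unassigned.

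**Week 105.** The protocol's schedule has Day 735 ± 3 (Days 732–738) and the SAP has Day 736 ± 3 (Days 733–739). A visit on Day 732 is allowed by the first and unassigned by the second.

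**Contiguous windows.** With Week 39 at Day 274, target ± 10 gives 21-day windows that meet exactly: Week 3 is Days 12–32, Week 6 is Days 33–53, and so on to Week 105, Days 726–746, with no unassigned day between. With Week 39 left at Day 272, ±10 fails. Week 36 (Days 243–263) and Week 39 (Days 262–282) overlap on Days 262–263, and Days 283–284 are open before Week 42 (Days 285–305).

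**The case against.** The strongest reply is that the windows copy the protocol's visit allowance, so apart from Week 39 (and one day at Week 105) a visit made on time is always assigned. The uncovered days are then mostly days on which no scheduled visit should occur. That stands, and it rules out three stronger readings that a reader might infer:

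- **That about 47% of safety data are lost.** The percentage counts calendar days, not assessments. Turning it into a share of data needs the distribution of visit and EoT days, which the documents do not give. The share could be very small.
- **That the tables are selected towards patients who tolerated treatment.** The documents do not show that delays are mainly due to toxicity, or that a delay moves all later visits. The anaemia and TSH rules interrupt IMP and bring the patient back within 7 or 5 days; they do not reschedule later visits. The only mention of delayed cycles (Protocol 5.2.1.2) concerns imaging, which must keep to the schedule from randomisation.
- **That safety signals would be missed.** Treatment-emergent and special-interest event tables do not use the windows. Worst post-baseline CTCAE grade and maximum QTcF shift tables are planned, and SAP 12.0 keeps unscheduled values for worst-case results. Listings are unaffected.

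Two further points also have force. SAP 12.0 sends unscheduled values to listings apart from worst-case results, so keeping those out of by-visit tables is partly a stated choice. It still sits awkwardly with 10.4 and with the sentence before it, and it does not settle EoT or late scheduled visits. Second, the SAP nowhere says that gap values are dropped; that is inferred from their having no analysis visit. The table shells, which are not available here, might say more.

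**Conclusion.** The point holds as a defect of specification. The rule in SAP 10.4 that all visits are windowed cannot be carried out with Table 1: typically 10 of every 21 days have no visit, EoT has no row, and no rule covers values between windows. EoT assessments in a gap, and scheduled visits more than 5 days off target that land in one, have no place in the by-visit laboratory, vital-sign and ECG summaries. The Week 39 target is a separate small error that leaves out otherwise on-time visits on Days 278 and 279.

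The number of values affected is unknown. The consequence is confined to descriptive by-visit safety summaries; neither the primary endpoint nor the adverse event tables depend on these windows. The point is minor but cheap to correct.

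This rests on three assumptions: that a value with no analysis visit is not tabulated, that the 5-day allowance is counted around fixed days from Day 1, and that the allowance in the protocol reviewed (Version 4.0) is unchanged in Version 5.0, which the SAP cites.

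**What to change.** In SAP 10.4 and Table 1:

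1. Set the Week 39 target to Day 274.
2. Replace the safety windows with contiguous midpoint-to-midpoint windows, which is ±10 days on the corrected grid, and start the first post-baseline window on Day 2 (Week 3 then covers Days 2–32).
3. Keep the closest-to-target rule and the preference for scheduled over EoT values.
4. Reconcile 10.4 with 12.0 by saying whether unscheduled values can enter by-visit tables or only worst-case summaries and listings.
5. Reconcile the Week 105 day between the protocol (Day 735) and the SAP (Day 736). Contiguous windows make the difference harmless for assignment.

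The cost is one SAP table, a sentence or two of text and the windowing program; no data collection changes. The small downside is that some tabulated values will lie up to 10 days from the nominal day, and up to 20 in the first window (Day 2 against Day 22). Where a value nearer the target exists, the closest-to-target rule will normally select it.

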5.3.4 Breastfeeding

Breastfeeding women will be excluded from the study.

5.3.5 12-lead Electrocardiogram

12-lead ECG will be obtained as outlined in Table 1.

At Visit 2 (Study Day 1) and Visit 3, 12-lead ECG will be recorded pre-dose and 2 hours (± 30 minutes) post setanaxib/placebo dosing. From Visit 4 onwards, 12-lead ECG are only required before setanaxib/placebo dosing; additional ECGs may be recorded as clinically indicated.

The ECGs will be conducted in the supine position after 5 minutes' rest.

The ECG tracing printout should be signed and dated by the person who made the interpretation locally (for purposes of patient safety management); the tracing printout will be archived at the study site. The machines will provide heart rate, PR, QRS, QT, and QTc intervals. If the ECG tracing printouts are in a non-archivable quality, including fading ink, a certified copy should be printed, signed and dated by the person who made the copy and labelled "certified copy". Electronically archived ECG tracings are acceptable as source data provided the electronic archival system is validated.

If there is any evidence of the cardiac conditions or abnormalities noted in Section 4.3.1, IMP is to be permanently discontinued.

Further details regarding the ECG assessments are provided in the site operations manual or manual provided by the vendor.

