10.0 Conventions and Derivations

10.1 Baseline, Change and Percent Change from Baseline

Baseline is defined as the last non-missing value before the first dose of IMP. Baseline values will generally be assessed at the Day 1 visit, the exception to this is the Initial tumour imaging scan which will be performed within 35 days prior to the date of treatment and will be used as the Baseline scan for the tumour assessments. For re-screened patients, the value associated with their screen failure record will not be considered for baseline.

If time of assessment is not collected and the assessment is collected on the same date as the first dose, the assessment will be assumed to be per protocol, i.e. prior to first dose. If multiple continuous assessments occur on the same day as first dose and no time is recorded, the average value will be used as baseline.

Change from baseline at any post-baseline time point will be defined as:

- Absolute Change from Baseline = (Value at Post Baseline Time Point Value at Baseline)
- Ratio of Postbaseline to Baseline = $\left(\frac{Value \ at \ Post \ Baseline \ Time \ Point}{Value \ at \ Baseline}\right)$

Percentage change from baseline at any post-baseline time point will be defined as:

• Percentage Change from Baseline = $100 * \left(\frac{Value \ at \ Post \ Baseline \ Time \ Point-Value \ at \ Baseline}{Value \ at \ Baseline}\right)$

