12.6.5 Physical Examinations, ECGs, and Other Observations Related to Safety

The absolute values and change from baseline values of each ECG parameter (Mean Heart Rate, PR Interval, QRS duration, QT interval, RR interval (see Section 10.11) and QTcF) will be summarised using univariate statistics at each analysis visit by treatment group. The interpretation of the ECG will be presented by result category (Abnormal Clinically Significant, Abnormal Non-Clinically Significant, Normal, Unevaluable and Unknown) at each analysis visit.

The absolute and change from baseline values for QTcF intervals will be further summarised using categorical intervals (see Section 10.11). Shift tables from baseline absolute interval to the maximum post baseline interval and maximum change from baseline interval will be presented.

All 12-lead ECG data will be provided in a listing, with abnormal interpretations flagged.

All physical examination findings will be provided in a listing only.

Baseline ECOG performance status will be summarised as part of the baseline characteristics, all ECOG data will be listed. The grading of ECOG performance status is defined in Section 10.12.

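### SAP 10.4 takes the worst qualitative result at Baseline and calls it conservative; at Baseline it is anti-conservative for safety and can conflict with the Baseline definition in SAP 10.1

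*SAP*

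**What the plan says.** SAP 10.1 sets the general definition: "Baseline is defined as the last non-missing value before the first dose of IMP". For a same-day assessment whose time is not collected, "the assessment will be assumed to be per protocol, i.e. prior to first dose". It adds: "If multiple continuous assessments occur on the same day as first dose and no time is recorded, the average value will be used as baseline".

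SAP 10.4 then gives rules for multiple records.

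- Quantitative, Baseline: "If more than one quantitative measurement meets the Baseline definition (Section 10.1), then then the arithmetic mean of the assessments will be calculated". This rule refers back to 10.1.
- Qualitative, Baseline and later: the worst result is taken when more than one "falls within a baseline or post-baseline visit window, then a conservative approach will be taken by selecting the worst result". This rule does not refer to 10.1.
- ECGs on Study Days 1 and 22: "Where multiple assessments occur on the same day in these instances, the timepoint will be preserved". This is a sub-bullet of the rules for quantitative post-baseline measurements.

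SAP Table 1 lists Baseline and Day 1 as separate analysis visits, both with target day 1 and neither with a window width.

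Protocol Table 1 schedules an ECG at Screening and on Day 1. For Visits 2 and 3, Protocol 5.3.5 says that "12-lead ECG will be recorded pre-dose and 2 hours" after dosing. In SAP 12.6.5, "The interpretation of the ECG will be presented by result category" at each analysis visit. That section plans shift tables for QTcF intervals only, and a listing of all ECGs with abnormal interpretations flagged.

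**The concern.** Taking the worst of several results guards against missing harm when the results come after treatment starts. Applied before treatment, it makes the starting point look worse, so later visits look less like a deterioration. The SAP gives both uses the same label, conservative, and the label is wrong for the first.

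The rule can also return a different value from 10.1 for the same patient, and the SAP does not say which section governs.

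This matters most for ECG interpretation. Clinically significant ECG abnormality is a named safety endpoint, and Protocol Table 2 lists QT prolongation and atrioventricular block among the preclinical findings. A finding that is judged by the reader and is not a QTcF value would appear in the by-visit interpretation table, where readers will naturally compare the Baseline row with later rows.

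**Working it through.** No figure in the plan depends on this rule, so there is none to reproduce. The check has three parts.

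**1. Do the two rules differ?** Take a patient with an abnormal Screening ECG and a normal Day 1 pre-dose ECG.

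- SAP 10.1, last value before first dose: Baseline is normal.
- SAP 10.4, worst qualitative result, if both records fall in the baseline window: Baseline is abnormal.

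Whether both records fall in that window cannot be settled from the text, because SAP Table 1 gives Baseline a target day and no width. If the Screening record is outside it, the usual Baseline is one pre-dose ECG and the worst-result rule seldom acts.

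**2. How large could the inflation be?** Let q be the probability that a single read is abnormal, with two reads per patient. Both q and the agreement between reads are assumptions; the documents give neither.

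For independent reads, P(Baseline abnormal) = 1 − (1 − q)². At q = 0.20 this is 1 − 0.80² = 0.36.

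For correlated reads, use a latent bivariate normal with correlation ρ: P = 1 − Φ₂(z, z; ρ), where z = Φ⁻¹(1 − q). At q = 0.20, z = 0.842. Then ρ = 0.5 gives 1 − 0.687 = 0.313, and ρ = 0.8 gives 1 − 0.729 = 0.271.

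| Assumed q | Single read | Worst of 2, ρ = 0 | ρ = 0.5 | ρ = 0.8 | Perfect agreement |
|---|---|---|---|---|---|
| 0.10 | 10% | 19% | 17% | 14% | 10% |
| 0.20 | 20% | 36% | 31% | 27% | 20% |
| 0.30 | 30% | 51% | 44% | 39% | 30% |

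**3. Which outputs does it reach?**

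- ECG interpretation by visit (SAP 12.6.5): reached, in the Baseline row, in both arms.
- QTcF summaries and shift tables: not reached. They come from a quantitative measure, which follows the averaging rule.
- Setanaxib against placebo at any post-baseline visit: not reached. The rows for those visits do not use Baseline.
- Listing of abnormal ECGs: not reached.
- ECOG: Protocol Table 1 schedules it at Screening and Day 1 only. Baseline ECOG could be reported as worse than the Day 1 value, but there is no scheduled later value to compare it with.

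**The case against.** The strongest reply is that the sentence is only a tie-break. SAP 10.1 says that Baseline values are generally taken at Day 1, and Table 1 sets target day 1. On that reading the Screening ECG is outside the window, one pre-dose read remains, and 10.1 and 10.4 do not clash. This is a fair reading, and it is why the conflict is described as possible. The text does not secure it, because no window is given and the qualitative sentence, unlike the quantitative one before it, does not refer to 10.1.

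The assumed rates can also be challenged. Exclusion criterion 18 removes patients with QTc above 450 ms (men) or 470 ms (women) and those with second- or third-degree block, so clinically significant conduction findings at Baseline may be rarer than 10% to 30%. That stands; the table shows sensitivity to assumptions and is not a forecast.

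Further, if timepoints were not kept apart for interpretations, Week 3 would also be a worst of two, because its ECGs are pre- and post-dose as well. That would offset the imbalance at Week 3. From Visit 4 onwards Protocol 5.3.5 requires only a pre-dose ECG, so it would not do so at later visits.

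Two stronger readings are tempting.

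- *A reader might infer that new ECG abnormalities on setanaxib are hidden.* The documents do not support this. No shift table is planned for interpretation, tables are by treatment group with placebo alongside, post-baseline worst results are retained, and abnormal ECGs are flagged in the listing.
- *A reader might infer that 10.1 lets the scheduled Day 1 post-dose ECG into the QTcF Baseline.* Section 10.1 requires a value before first dose, and 10.4 preserves the ECG timepoint. If an untimed pre-dose and an untimed 2-hour value were averaged, Baseline would move by half the 2-hour change (an assumed 10 ms would give 5 ms). That needs both the clock time and the timepoint label to be missing. The documents do not show whether clock time is collected.

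**Conclusion.** The point holds as a wrong label and an unresolved inconsistency in the SAP. Taking the worst qualitative result at Baseline is anti-conservative for safety, and it can contradict 10.1 with no stated precedence. Its practical reach is narrow: the Baseline row of one descriptive ECG table, in both arms, and the within-arm reading of that table over time. With two reads and an assumed 20% abnormal rate, that row would show 27% to 36% for latent correlations from 0.8 down to 0, and 20% if reads agree perfectly. No hypothesis test or primary result depends on it.

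Separately, the rule that preserves ECG timepoints sits under the quantitative post-baseline rules, so it does not expressly cover the Day 1 ECG interpretation. That is a gap to close, not a demonstrated error.

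**What to change.** In SAP 10.4, limit the worst-result rule to post-baseline windows. State that qualitative Baselines follow 10.1, the last non-missing result before first dose, and keep a tie-break only for records at the same last pre-dose time.

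Add that the preserved ECG timepoint on Study Days 1 and 22 also covers the interpretation. Add to 10.1 that an ECG labelled post-dose never counts as Baseline, even if its clock time is missing.

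The cost is a few sentences in the SAP and a small change to the Baseline derivation. No new data are needed.
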